While some patients with early stage breast cancer are able to achieve significant clinically meaningful loss, the majority are unable to. The goal of this project is to evaluate whether weight loss in overweight/obese breast cancer survivors whose trajectory suggests unlikelihood of attaining clinically significant weight loss of ≥5% with behavioral intervention alone can be augmented with pharmacotherapy. Studies have shown that self-directed weight loss is generally not successful. Our POWER-remote study showed that 89.1% of women in the self-directed arm were not successful in weight loss. With the implementation of remote behavioral intervention, this value drops to 54% of women not being able to lose at least 5% of their weight. We will focus on this population of women, as they may be identified earlier (after 4-12 weeks of behavioral intervention). Success for this study will be measured by the rate of these women who are able to achieve weight loss with the adapted behavioral intervention with pharmacotherapy. As there are over 3 million breast cancer survivors in the US⁵, many of whom are overweight/obese, underutilization of anti-obesity drugs may be a critical and neglected component of weight loss treatment.

We will evaluate the extent to which implementation of a chronic weight loss medication, Contrave® (Naltrexone/Bupropion), is associated with achieving \geq 5% weight loss. All patients will receive the POWER-remote behavioral weight loss intervention (BWL) and have a behavioral coach for the duration of the 6 month study. During months 1-3, the behavioral coach will call weekly. From months 4-6, the behavioral coach will call monthly. At week 9, those who lose \geq 5%, designated fast responders, will continue with BWL alone (FAST-BWL) while those

[figure not shown]
who lose <5%, designated slow responders, will continue BWL and initiate Contrave (SLOW-BWL). The SLOW-BWL arm will receive at least 16 weeks of Contrave (as per Federal Drug Administration [FDA] recommended administration) starting at week 9 and discontinue if ≥5% weight loss is not achieved at month 6. During month 3, all participants continue to have weekly calls with the behavioral coach and will be asked about symptoms, which may be related to initiation of pharmacotherapy; any symptoms are reported to the Protocol Chair for further evaluation. In addition to total weight loss, we will evaluate biomarkers associated with obesity, microbiome and cardiometabolic factors.

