Because obesity is already a strong risk factor for cardiovascular disease, cancer treatment in obese patients can further increase overall risk for adverse cardiac effects ³². A recent meta-analysis suggests that being overweight or obese may be risk factors for cardiotoxicity from anthracyclines, especially in sequence with trastuzumab ³³. Other studies have found obesity to be associated with an increased risk of cardiac dysfunction in women using trastuzumab ³⁴. Additionally, in elderly patients (over 65 years), obesity is an independent risk factor for trastuzumab-related cardiac toxicity ³⁵.

About one third of breast cancer survivors have chronic fatigue and about one fourth will have persistent fatigue after two years ³⁶. Although the development of fatigue in breast cancer patients seems largely impacted by cancer therapy, the long-term persistence of fatigue is related to preexisting medical conditions and lifestyle factors. Higher BMI at baseline is significantly associated with increased physical fatigue during and after cancer treatment ³⁷. The Mammary carcinoma Risk factor Investigation (MARIE) study demonstrated that both physically inactive lifestyle and obesity were associated with persistent physical fatigue, independent of chemotherapy and radiation ³⁸. In a study of patients who were overweight or obese, fatigue after chemotherapy lower in an exercise group versus a non-exercise group ³⁹. Higher BMI, associated with greater tendencies to catastrophize about fatigue and amplify physical symptoms, was predictive of fatigue at beyond nine months ⁴⁰. These studies demonstrate the importance of an ideal body weight as chronic fatigue is associated with emotional distress and limits function and willingness to exercise.

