7.3 Visits and Follow up

The study will include a 24-month recruitment period, a 6-month implementation period, which involve 3 in-person visits and at least 16 phone sessions for each participant. We anticipate enrolling 2-4 participants per month. All women will receive the POWER remote behavioral weight loss intervention (BWL) and a behavioral coach. They will all receive lifestyle guidelines (See Appendix B). At week 9, those who lose ≥5%, designated fast responders, will continue with BWL alone (FAST-BWL) while those who lose <5%, designated slow responders, will receive BWL with the addition of Contrave (SLOW-BWL).

Women in SLOW-BWL will initiate Contrave one 8-mg naltrexone/90-mg bupropion tablet per day and increased over 3 weeks to the maintenance dosage of two 8-mg/90-mg tablets twice daily, for a total daily dose of 32mg/360mg. It should be taken by mouth in the morning and in the evening and should not be cut, chewed, or crushed. In clinical trials, Contrave was administered with meals. However, it should not be taken with a high-fat meal because of a resulting significant increase in bupropion and naltrexone systemic exposure. As patients are instructed to follow the DASH (Dietary Approaches to Stop Hypertension) and/or Mediterranean diet, this should not be an issue. Patients will be instructed that ketogenic and low carbohydrate diets would impact the absorption of Contrave.

The behavioral coach will review the weekly weight and new symptoms entry (patient will completed in REDCap survey or via telephone if not done) for months 3-6 for participants in both arms. The REDCap survey (Appendix C) asks patients about any new symptoms and includes examples of those which had a frequency of at least 4% in patients on Contrave in clinical trials. Any new symptoms noted will be directed to the Protocol Chair for further evaluation. If patients on Contrave have significant adverse effects, providers will decrease the dose by 50% and assess tolerability over 1 week. If symptoms are alleviated, patient can

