continue at lowered dose. If symptoms persist, dose can be lowered by 50% again. If symptoms are alleviated, patient can continue at lowered dose. However, if symptoms persist, the medication should be discontinued and the patient should continue with BWL alone. Following the prescribing information, Contrave will be discontinued for patients who do not achieve \geq 5% and seen in person once a month to assess compliance and potential side effects.

The weight loss intervention is based on the remote-support arm of the POWER trial that was also used by our team in a previous study in breast cancer survivors^{3,4}. It involves two main components: an online portion that participants access on their computer or phone and a telephone/teleconferencing portion to help monitor progress and deliver the behavioral intervention. All participants will receive the POWER intervention, which will be remote and last 6 months. Participants will be given a physical activity monitor (Fitbit) that encourages increased activity by measuring steps and process variables, such as heart rate and sleep. Participants will use a web-based platform to access learning materials and log their diet and exercise each day. They will also record their weight once weekly through our survey. As participants monitor their own progress, they will receive telephone/teleconferencing calls on a regular schedule by a weight loss coach to help monitor and guide progress utilizing dietary, physical activity and weight information. All contacts will be phone/teleconferencing based and last about 30 minutes. For all participants, contacts will occur weekly during the first 3 months (a baseline visit followed by 12 phone sessions) and monthly for the remaining 3 months (3 phone sessions). At the conclusion of the study after 6 months of behavioral intervention, participants will have an in-person visit.

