7.6.5 Participant contact

Participants receive teleconferencing/telephone calls weekly for 3 months and monthly thereafter from lifestyle coaches to encourage completion of learning materials modules, to reinforce key learning points, and to encourage logging and provide feedback on weight, food intake, and exercise tracking. Calls will be each week for months 1-3, once a month for months 4-6. Each call will be approximately 30-45 minutes long. For all participants, coaches will also review and/or inquire about any new symptoms (weekly during months 4-6) and adherence if they are assigned to the arm with the pharmacotherapy. If symptoms are reported, the coach will notify the physician on study and the patient may be contacted by the physician for further evaluation.

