10.3 Definitions

• Adverse event (AE): Any undesirable sign, symptom or medical condition occurring after starting therapy even if the event is not considered to be related to the study. An undesirable medical condition can be symptoms (e.g., nausea, chest pain), signs (e.g.,

tachycardia) or the abnormal results of an investigation (e.g., laboratory findings, biopsies).

Medical conditions/diseases present before starting study treatment are only considered adverse events if they worsen after starting study treatment (any procedures specified in the protocol). Adverse events occurring before starting study treatment but after signing the informed consent form will be recorded. Abnormal laboratory values or test results constitute adverse events only if they induce clinical signs or symptoms or require therapy.

Serious adverse event or reaction: Any untoward medical occurrence secondary to therapy that: results in death, is immediately life-threatening, requires inpatient hospitalization or prolongation of existing hospitalization, results in persistent or significant disability / incapacity, or is an important medical event that may jeopardize the subject or may require medical intervention to prevent one of the outcomes listed above.

The definition of serious adverse event (experience) also includes *important medical* event. Medical and scientific judgment should be exercised in deciding whether expedited reporting is appropriate in other situations, such as important medical events that may not be immediately life-threatening or result in death or hospitalization but may jeopardize the patient or may require intervention to prevent one of the other outcomes listed in the definition above. These should also usually be considered serious.

A hospitalization planned before the start of the study agent(s) and/or for a preexisting condition that has not worsened does not constitute a serious adverse event (e.g., elective hospitalization for breast reconstruction of the ipsilateral breast). A hospitalization for a social reason in the absence of an adverse event also does not meet the criteria for a serious adverse event.

- Unexpected adverse event: An adverse event, which varies in nature, intensity or frequency from information on the investigational intervention provided in the Investigator's Brochure, package insert or safety reports. Any adverse event that is not included in the informed consent is considered "unexpected".

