APPENDIX C: Weekly weight and symptom survey

During the behavioral intervention, coaches call patients weekly the first 3 months, followed by monthly for months 4-6. Patients will receive a REDCap survey on a weekly basis with the following question:

1) What is your v	weight this week?
*If patients have not o	completed this survey before the call with the coach, the coach may enter
the data that is conve	yed verbally.

During months 3-6, ALL study participants will continue with weekly survey, in addition to a question about any new symptoms:

2) During the past 7 days, have you experienced any new symptoms (such as abdominal pain, anxiety, constipation, diarrhea, dizziness, dry mouth, fatigue, gastroenteritis, headache, hot flush, insomnia, nausea, tremor, vomiting etc.)?

^{*}If patients have not completed this survey before the call with the coach, the coach may enter the data that is conveyed verbally.

^{**}The coordinator will review all new symptom entries in the REDCap survey on a weekly basis, and new symptoms will be reported to the PI for further evaluation.

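### After Contrave titration, the routine weekly symptom inquiry covers only new symptoms, although section 10.3 counts worsening of an existing condition as an adverse event

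*Combined protocol and SAP*

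**What the plan says.** Appendix C adds a symptom question to the weekly survey for all participants in months 3 to 6: "During the past 7 days, have you experienced any new symptoms". Its examples include fatigue, hot flush, insomnia, anxiety, headache and dizziness. The note beneath it forwards the same restricted set: "new symptoms will be reported to the PI for further evaluation".

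The body text repeats the restriction. Section 7.3 states: "Any new symptoms noted will be directed to the Protocol Chair for further evaluation". Section 7.6.5 has the coach review or ask about new symptoms weekly in months 4 to 6, and section 13.1 has new symptoms reviewed together with the drug logs after titration. None of these sections defines *new* or says what it is measured against.

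The adverse-event definition in section 10.3 is wider: "Medical conditions/diseases present before starting study treatment are only considered adverse events if they worsen after starting study treatment". Worsening therefore counts. The Summary is also wider when it describes the month-3 calls: "any symptoms are reported to the Protocol Chair for further evaluation".

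**The concern.** Several of the survey's example symptoms may already be present when Contrave starts. Section 5.4 says: "About one third of breast cancer survivors have chronic fatigue". Section 7.6 names fatigue and hot flashes among the effects expected from prior or ongoing cancer therapy. For a woman who already has such a symptom, a drug effect appears as worsening. If she reads the survey question literally, she answers no, although section 10.3 would count the event.

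Two things are at stake. One is the completeness of the safety summary that section 13.2 promises throughout the study. The other is whether ongoing intolerance reaches the Protocol Chair. The Summary says these drugs have not been studied alongside hormonal therapy, so symptoms that endocrine treatment and Contrave may share are the ones on which this trial could inform.

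**Working it through.** No design figure depends on this point. The check compares the sections and adds one illustrative product.

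**Step 1. Instrument against definition.** The survey question, the note on forwarding, 7.3, 7.6.5 and 13.1 all cover new symptoms only. Section 10.3 covers new conditions and worsening of old ones. The routine instrument is narrower than the definition it serves.

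**Step 2. What else could pick up worsening, and when.**

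| Channel | Scope | Timing |
|---|---|---|
| Drug diary (7.6.6, Appendix G) | Side effects, not limited to new ones | Titration month in 7.6.6; the Appendix G form continues from week 4 onward |
| Coach calls (Summary) | Symptoms in general | Month 3 |
| In-person check (7.3) | Potential side effects | Monthly, but absent from the visits in 7.3.3 and from the calendar in section 8 |
| Contact with the research nurse (10.2.6) | Symptoms in general | Only if the woman makes contact |
| Patient-reported outcomes (7.5.2, Appendices E and F) | Fatigue, anxiety, sleep, hot flashes, headache, dizziness, vomiting and diarrhea, among others | Baseline, 2 months and 6 months |
| Weekly survey and coach review (Appendix C, 7.3, 7.6.5) | New symptoms only | Weekly; months 3 to 6 in Appendix C and 7.3, months 4 to 6 in 7.6.5 |

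On the 7.6.6 reading of the diary, the last row is the only scheduled symptom inquiry after titration whose existence and timing are not in doubt for that period.

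**Step 3. Length of that period.** The Summary gives at least 16 weeks of Contrave and section 13.1 a 4-week titration: 16 − 4 = at least 12 weeks. This agrees with the 3 months at constant dose in 13.1.

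**Step 4. Illustration for one symptom.** Section 13.1 expects 55% of 55 women in SLOW-BWL: 0.55 × 55 = 30.25, about 30. Section 5.4 gives about one third with chronic fatigue and about one fourth with persistent fatigue after two years.

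- 30 × 1/4 = 7.5, about 8 women
- 30 × 1/3 = 10 women

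These would be women with fatigue before the drug, not women harmed by it. The calculation assumes that the general survivor rate applies to a cohort with ECOG status 0 to 1, where it may be lower. The documents give no corresponding rates for hot flushes, insomnia, anxiety or headache.

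**Step 5. Direction.** Restricting the question can leave events out but cannot add any. Any effect of the wording on the event count is therefore downward. Its size cannot be derived from the documents.

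**The case against.** The strongest reply is that the survey is only one of several feeders. Section 10.1 collects related events whether they are volunteered, found on questioning or detected by other means. The diary covers dose escalation, when section 10.2.6 says nausea is typically first reported. The questionnaires measure several of the same symptoms before and after the drug, and Appendix F flags worsening of 5 points on the PROMIS scales and 4.6 on the endocrine scale. All of this stands. A reader might infer that worsening is asked about nowhere in the protocol, and the documents do not support that.

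A reader might also infer that no pre-drug answers exist. That is not established. The symptom question begins in month 3 and Contrave at week 9, so the first survey, looking back 7 days, may precede the first dose. Section 7.6.8 even places the drug in months 4 to 6. The 2-month questionnaires give a further reference. What is missing is a statement of the order.

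A third tempting reading is that the survey's silence on continuing symptoms disables the section 7.3 step "if symptoms persist, the medication should be discontinued". It does not. Once an adverse effect is known, section 7.3 has providers assess tolerability, and nothing there makes the survey their source. A persisting effect was also new when it began. What the weekly record loses is duration and later severity.

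The reply does not close the gap after titration. The questionnaires have no time point between the 2-month visit and month 6, and the printed items do not cover nausea, constipation, dry mouth or tremor. Nurse contact depends on the woman. The monthly check is not in the schedule. If the diary does run to the end of treatment, the gap narrows considerably, but 7.6.6 says otherwise.

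**Conclusion.** The point holds for the period after titration. The weekly survey and coach review ask only about new symptoms, while section 10.3 also counts worsening. For at least 12 weeks on Contrave, worsening of a symptom already present would be found only by self-report, by a monthly check that the visit schedule does not contain, or at month 6. The safety summary may under-count such events.

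How many is unknown. The figure of 8 to 10 of 30 women shows only how many might start with fatigue if the general survivor rate applied. The conclusion rests on two assumptions: that the diary stops after titration, as 7.6.6 says, and that at least some women read *new* literally. The primary endpoint, sample size, power and type I error are untouched. This is an inexpensive improvement to safety ascertainment and does not challenge the design.

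**What to change.** - In Appendix C question 2, and in 7.3, 7.6.5 and 13.1, ask about new, worsening or continuing symptoms and record which of the three applies. Word the forwarding note in Appendix C to match.
- State that the week-9 survey is completed before the first dose and serves as each woman's reference.
- Reconcile the Summary, 7.3, 7.6.5, 7.6.6, Appendix C and Appendix G on what is asked, in which months, how long the diary runs, and whether the monthly in-person check exists alongside the visits in 7.3.3 and section 8.

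The cost is one edited REDCap question and matching protocol text, with no added visits or staff. The coordinator will have somewhat more entries to review and pass on.

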APPENDIX D: Aim for a Healthy Weight Brochure

Participants who are not eligible for the study at the screening visit will be provided the NHLBI publication "Aim for A Healthy Weight."

The publication is publically available and will be downloaded from the National Institutes of Health's website to be given to study participants:

http://www.nhlbi.nih.gov/health/public/heart/obesity/aim hwt.pdf

APPENDIX E: PRO Questionnaire

The following represents the questions to be asked in the REDCap survey.

CLINICAL AND DEMOGRAPHIC INFROMATION

T	T.	
I.	Demograp)hics:
		,,,,,,,,,,,,,,,,,,,,,,,,,,,,,,,,,,,,,,,

- a. What is your date of birth?
- b. What is your age?
- c. Are you Hispanic or Latino?
 - i. Yes
 - ii. No
- d. What is your race?
 - i. White/Caucasian
 - ii. Black or African American
 - iii. Asian
 - iv. Native Hawaiian or Pacific Islander
 - v. American Indian or Alaska Native
 - vi. Other, _____

II. Past Medical/social/family history

- 1. Have you had a menstrual period in the past 12 months?
 - a. Yes
 - b. No
- 2. If you have not had a menstrual period in the last 12 months, at what age did you stop having periods? (free text)
- 3. During the past year how many alcoholic beverages did you have?
 - a. Never or less than 1 per month
 - b. 1-3 per month
 - c. 1 per week
 - d. 2-4 per week
 - e. 5-6 per week
 - f. 1 per day
 - g. 2-3 per day
 - h. 4-5 per day

- i. More than 5 per day
- 4. Have you ever smoked?
 - a. Yes
 - b. No
- 5. If you have ever smoked, please indicate how many cigarettes you smoked when you were smoking:
 - a. Never smoked
 - b. Less than one-half pack per day
 - c. One-half to one pack per day
 - d. Two packs per day
 - e. Three packs per day
 - f. More than three packs per day
- 6. If you have ever smoked, please indicate how many years you smoked:
 - a. One year
 - b. 2-5 years
 - c. 6-10 years
 - d. 11-15 years
 - e. 16-20 years
 - f. 21-25 years
 - g. 26-30 years
 - h. 31-35 years
 - i. >35 years

III. Medications

- 1. Which of the following medications are you taking? (Select all that apply)
 - a. Tamoxifen
 - b. Raloxifene (Evista)
 - c. Anastrozole (Arimidex)
 - a. Letrozole (Femara)
 - b. Exemestane (Aromasin)
 - c. Goserelin (Zoladex)
 - d. Leuprolide (Lupron)

IV. Patient Reported Outcomes (PROs) - Sleep

In the	past month				
1.	During the past month, what time have you usually gone to bed at night?				
	I	BED TIME	-		
2.	2. During the past month, how long (in minutes) has it usually taken you to fall asleep each nig				
	1	NUMBER OF MINUTES	S		
3. During the past month, what time have you usually gotten up in the morning?				morning?	
	(GETTING UP TIME			
4.	During the past month, how many hours of actual sleep did you get at night? (This may be different than the number of hours you spent in bed.)				
	I	HOURS OF SLEEP PER	NIGHT		
For eac	ch of the remaining q	uestions, check the one	best response. Please	answer all questions.	
5.	During the past month, how often have you had trouble sleeping because you				
a) Cannot get to sleep within 30 minutes					
	Not during the	Less than	Once or twice	Three or more	
	past month	once a week	a week	times a week	
b)	Wake up in the middle of the night or early morning				
	Not during the	Less than	Once or twice	Three or more	
	past month	once a week	a week	times a week	
c)	Have to get up to u	se the bathroom			
	Not during the	Less than	Once or twice	Three or more	
	past month	once a week	a week	times a week	
d)	Cannot breathe comfortably				
	Not during the	Less than	Once or twice	Three or more	
	past month	once a week	a week	times a week	
e)	Cough or snore lou	Cough or snore loudly			
	Not during the	Less than	Once or twice	Three or more	
	past month	once a week	a week	times a week	

f)	Feel too cold				
	Not during the	Less than	Once or twice	Three or more	
	past month	once a week	a week	times a week	
g)	Feel too hot				
	Not during the	Less than	Once or twice	Three or more	
	past month	once a week	a week	times a week	
h)	Had bad dreams				
	Not during the	Less than	Once or twice	Three or more	
	past month	once a week	a week	times a week	
i)	Have pain				
	Not during the	Less than	Once or twice	Three or more	
	past month	once a week	a week	times a week	
	How often during the past month have you had trouble sleeping because of this?				
	_	Less than	Once or twice	Three or more	
	past month	once a week	a week	times a week	
7.	During the past month, how would you rate your sleep quality overall?				
		Very good			
		Fairly good			
		Fairly bad			
		Very bad			
8.	During the past month the counter")?	n, how often have you take	en medicine to help you	u sleep (prescribed or "over	
	Not during the	Less than	Once or twice	Three or more	
	past month	once a week	a week	times a week	

8. During the past month, how often have you had trouble staying awake while driving, eating meals, or engaging in social activity?

	Not during the	Less than	Once or twice	Three or more
	past month	once a week	a week	times a week
9.	During the past r to get things don		blem has it been for you t	o keep up enough enthusiasm
	No pi	oblem at all		
	Only	a very slight problem		
		what of a problem		
		y big problem		
	71 (61	y oig prootein		
, D		(PDO) PI	. 15	
. Pa	tient Reported U	outcomes (PROs) – Phy	ysical Function	
1.				ch as running, lifting heavy
	a. Not at all	ting in strenuous sports	?	
	b. Very littl			
	c. Somewha			
	d. Quite a lo			
	e. Cannot d	0		
2.	Does your health	ı now limit you in walki	ng more than a mile?	
۷.	a. Not at all	•	ing more than a nine:	
	b. Very littl			
	c. Somewha			
	d. Quite a lo	ot		
	e. Cannot d	0		
3.	Does your health	now limit you in climb	oing one flight of stairs	?
	a. Not at all	 	88	
	b. Very littl	e		
	c. Somewha	at		
	d. Quite a lo	ot		
	e. Cannot d	o		
4.	Does your health	ı now limit you in lifting	g or carrying groceries?)
••	a. Not at all	•	J 	
	b. Very littl			
	c. Somewha			
	d Onite a la	nt .		

- e. Cannot do
- 5. Does your health now limit you in bending, kneeling or stooping?
 - a. Not at all
 - b. Very little
 - c. Somewhat
 - d. Quite a lot
 - e. Cannot do
- 6. Are you able to do chores such as vacuuming or yard work?
 - a. Without any difficulty
 - b. With a little difficulty
 - c. With some difficulty
 - d. With much difficulty
 - e. Unable to do
- 7. Are you able to dress yourself, including tying shoelaces and doing buttons?
 - a. Without any difficulty
 - b. With a little difficulty
 - c. With some difficulty
 - d. With much difficulty
 - e. Unable to do
- 8. Are you able to shampoo your hair?
 - a. Without any difficulty
 - b. With a little difficulty
 - c. With some difficulty
 - d. With much difficulty
 - e. Unable to do
- 9. Are you able to wash and dry your body?
 - a. Without any difficulty
 - b. With a little difficulty
 - c. With some difficulty
 - d. With much difficulty
 - e. Unable to do
- 10. Are you able to get on and off the toilet?
 - a. Without any difficulty
 - b. With a little difficulty
 - c. With some difficulty
 - d. With much difficulty
 - e. Unable to do

VI. Patient Reported Outcomes (PROs) - Anxiety

In the past 7 days......

- 1. I felt fearful
 - a. Never
 - b. Rarely
 - c. Sometimes
 - d. Often
 - e. Always
- 2. I felt anxious
 - a. Never
 - b. Rarely
 - c. Sometimes
 - d. Often
 - e. Always
- 3. I felt worried
 - a. Never
 - b. Rarely
 - c. Sometimes
 - d. Often
 - e. Always
- 4. I found it hard to focus on anything other than my anxiety
 - a. Never
 - b. Rarely
 - c. Sometimes
 - d. Often
 - e. Always
- 5. I felt nervous
 - a. Never
 - b. Rarely
 - c. Sometimes
 - d. Often
 - e. Always
- 6. I felt uneasy
 - a. Never
 - b. Rarely
 - c. Sometimes
 - d. Often
 - e. Always

- 7. I felt tense
 - a. Never
 - b. Rarely
 - c. Sometimes
 - d. Often
 - e. Always

VII. Patient Reported Outcomes (PROs) - Depression

In the past 7 days....

- 1. I felt worthless
 - a. Never
 - b. Rarely
 - c. Sometimes
 - d. Often
 - e. Always
- 2. I felt that I had nothing to look forward to
 - a. Never
 - b. Rarely
 - c. Sometimes
 - d. Often
 - e. Always
- 3. I felt helpless
 - a. Never
 - b. Rarely
 - c. Sometimes
 - d. Often
 - e. Always
- 4. I felt sad
 - a. Never
 - b. Rarely
 - c. Sometimes
 - d. Often
 - e. Always
- 5. I felt like a failure
 - a. Never
 - b. Rarely
 - c. Sometimes
 - d. Often

- e. Always
- 6. I felt depressed
 - a. Never
 - b. Rarely
 - c. Sometimes
 - d. Often
 - e. Always
- 7. I felt unhappy
 - a. Never
 - b. Rarely
 - c. Sometimes
 - d. Often
 - e. Always
- 8. I felt hopeless
 - a. Never
 - b. Rarely
 - c. Sometimes
 - d. Often
 - e. Always

VIII. Patient Reported Outcomes (PROs) - Pain

In the past 7 days.....

- 1. How much did pain interfere with your enjoyment of life?
 - a. Not at all
 - b. A little bit
 - c. Somewhat
 - d. Quite a bit
 - e. Very much
- 2. How much did pain interfere with your ability to concentrate?
 - a. Not at all
 - b. A little bit
 - c. Somewhat
 - d. Quite a bit
 - e. Very much
- 3. How much did pain interfere with your day to day activities?
 - a. Not at all
 - b. A little bit
 - c. Somewhat

- d. Quite a bit
- e. Very much
- 4. How much did pain interfere with your enjoyment of recreational activities?
 - a. Not at all
 - b. A little bit
 - c. Somewhat
 - d. Quite a bit
 - e. Very much
- 5. How much did pain interfere with your doing tasks away from home (eg. getting groceries, running errands)?
 - a. Not at all
 - b. A little bit
 - c. Somewhat
 - d. Quite a bit
 - e. Very much
- 6. How often did pain keep you from socializing with others?
 - a. Never
 - b. Rarely
 - c. Sometimes
 - d. Often
 - e. Always

IX. Patient Reported Outcomes (PROs) - Fatigue

In the past 7 days....

- 1. How often did you feel tired?
 - a. Never
 - b. Rarely
 - c. Sometimes
 - d. Often
 - e. Always
- 2. How often did you experience extreme exhaustion?
 - a. Never
 - b. Rarely
 - c. Sometimes
 - d. Often
 - e. Always
- 3. How often did you run out of energy?
 - a. Never

- b. Rarely
- c. Sometimes
- d. Often
- e. Always
- 4. How often did your fatigue limit you at work (include work at home)?
 - a. Never
 - b. Rarely
 - c. Sometimes
 - d. Often
 - e. Always
- 5. How often were you too tired to think clearly?
 - a. Never
 - b. Rarely
 - c. Sometimes
 - d. Often
 - e. Always
- 6. How often were you too tired to take a bath or shower?
 - a. Never
 - b. Rarely
 - c. Sometimes
 - d. Often
 - e. Always
- 7. How often did you have enough energy to exercise strenuously?
 - a. Never
 - b. Rarely
 - c. Sometimes
 - d. Often
 - e. Always

X. Patient Reported Outcomes (PROs) – MOS Sexual Function Scale

	Not a	Little of a	Somewhat of a	Very much of	Not
Lack of sexual	problem	problem	problem	a problem	applicable
interest					
	1	2	3	4	5

Unable to relax and enjoy sex			Somewhat of a problem	•	Not applicable
enjoy sex	1	2	3	4	5
Difficulty in becoming sexually	Not a problem	Little of a problem	Somewhat of a problem	•	Not applicable
aroused	1	2	3	4	5
Difficulty in having an orgasm			Somewhat of a problem	•	Not applicable
un organii	1	2	3	4	5

XI. Patient Reported Outcomes (PROs) – Endocrine Symptoms FACT-ES

Please mark one number per line to indicate your response as it applies to the past 7 days.

	Not at all	A little bit		-	Very much
I have hot flashes	0	1	2	3	4
I have cold sweats	0	1	2	3	4
I have night sweats	0	1	2	3	4
I have vaginal discharge	0	1	2	3	4

I have vaginal itching/irritation	0	1	2	3	4
I have vaginal bleeding or spotting	0	1	2	3	4
I have vaginal dryness	0	1	2	3	4
I have pain or discomfort with intercourse	0	1	2	3	4
I have lost interest in sex	0	1	2	3	4
I have gained weight	0	1	2	3	4
I feel lightheaded (dizzy)	0	1	2	3	4
I have been vomiting	0	1	2	3	4
I have diarrhea (diarrhea)	0	1	2	3	4
I get headaches	0	1	2	3	4
I feel bloated	0	1	2	3	4
I have breast sensitivity/tenderness	0	1	2	3	4

I have mood swings	0	1	2	3	4
I am irritable	0	1	2	3	4
I have pain in my joints	0	1	2	3	4

XII. Godin Leisure-Time Exercise questionnaire

Please indicate the average amount of exercise you did in the last 7 days.

When answering these questions, please:

- note that the main difference between the 3 questions below is the intensity of the exercise.
- if you did not do any exercise in one of the categories, please write in "0".

Considering a typical week (7 days), how many times on average did you do the following kinds of exercise for more than 15 minutes during your free time?

For example, if you did fast walking for a total of 60 minutes over the past week, you would write 4.

	Times Per Week
STRENUOUS EXERCISE	
What is strenuous? HEART BEATS RAPII (e.g. running, jogging, hockey, soccer, squa swimming, vigorous long distance bicycling	sh, cross country skiing, vigorous
	Times Per Week
MODERATE EXERCISE	
What is moderate? NOT EXHAUSTING, I	•
What is moderate. NOT EXTROSTING, E	IGHT PERSPIRATION
